8.4. Randomization Criteria

Only those patients meeting all of the following randomization criteria at Visit 2 are eligible for randomization:

1. Continues to meet all inclusion and exclusion criteria, including urine and blood test results, and is successfully and consistently utilizing the diary system.
2. Patient's pain satisfies the following criteria, as assessed by diary pain scores (24-hour recall):
 - a. A mean worst daily Long COVID pain intensity score ≥ 4 and ≤ 9 on the 11-point (0–10) NRS for the 7 days immediately preceding Visit 2, and
 - b. No more than 2 individual days with a Long COVID pain score < 4 on the 7 days immediately preceding Visit 2, and
 - c. No score of 10 on any of the 7 days immediately preceding Visit 2, and
 - d. Long COVID pain scores recorded on at least 5 out of the 7 days immediately preceding Visit 2.

8.5. Patient Withdrawal Criteria

In accordance with the Declaration of Helsinki, patients have the right to withdraw from the study at any time for any reason. The Investigator and Tonix also have the right to remove patients from the study. Additional information regarding withdrawal or discontinuation of patients is described in detail in [Section 11.6.2](#).

9. TREATMENT OF PATIENTS

9.1. Prior and Concomitant Medications

Patients who are taking certain medications are eligible for the study if they are willing and able, and it is medically reasonable, for them to be withdrawn from these medications prior to randomization and then refrain from usage during this study. The specific medications that must be withdrawn include duloxetine, milnacipran, pregabalin, gabapentin and other forms of anticonvulsants, tramadol, tapentadol, amitriptyline and other tricyclic antidepressants, trazodone, narcotics/opioids, naltrexone (including CONTRAVE[®]), all other forms of cyclobenzaprine (AMRIX[®], or generic equivalents), orexin receptor antagonists, and benzodiazepines.

Therapies used to treat acute COVID-19 symptoms or severity, such as convalescent plasma, remdesivir, or dexamethasone will be prohibited.

Due to the exclusion of all opioids (including tramadol and tapentadol) during the treatment phase of the study, patients requiring opioids on a regular or frequent basis for any indication should not be considered. In addition, patients who are taking gabapentin, pregabalin, or any other anticonvulsant due to neuropathic pain should not be considered.

Other prescription or over-the-counter medication not specifically excluded by entry criteria may be continued during the study, provided that the patient has been on this medication at a stable dose for at least 4 weeks (except for allowed antidepressants, which require 90 days at stable dose) prior to randomization and is not expecting to change dosages during the period of the study.

In addition, certain other medications will also be prohibited and may require washout or exclusion of the patient if washout is not appropriate (eg, trazodone, mirtazapine, levomilnacipran, nefazodone, benzodiazepines, non-benzodiazepine sleep aids, stimulants, sodium oxybate, ketamine, esketamine, etc.).

Patients using teeth-whitening products such as whitening strips or prescription whitening products must agree to discontinue their use from the day of randomization until the end of their study participation.

After randomization, sedating antihistamines (eg, diphenhydramine, hydroxyzine) can be used as needed for insomnia; however, patients must be able to discontinue them during the Screening phase and must refrain from their use during the week of baseline data collection preceding Visit 2. The use of sedating anti-histamines after randomization should always be under the direction of the Investigator, and such use should be minimized to no more than a few nights in a row, followed by attempts to refrain from use.

The use of non-prescription nutraceuticals such as melatonin, ramelteon, and valerian root is not restricted.

New medications that are deemed required, in the opinion of the Principal Investigator or another physician, will be allowed, including medications needed to treat AEs. If there is a requirement for acute opioids, corticosteroids, or other treatments that could confound the evaluation of pain throughout the treatment period, the Investigator may consult with the Medical Monitor to

potentially delay the study visit until the medication is no longer needed. At a minimum, no opioid/narcotic should have been utilized within 2 days of a study visit, and ideally there will have been no usage during the 7 days prior to any visit, since important efficacy data will be collected on the diary during the week leading up to each visit.

Rescue medications used by patients throughout the study will be identified and documented during study visits.

9.2. Alcohol and Cannabis/THC Use

Patients utilizing cannabis/THC and alcohol are to be excluded if MINI 7.0.2 Module J criteria are met for greater than MILD Cannabis Use Disorder or greater than MILD Alcohol Use Disorder in Module I during the preceding 1 year (prior to the Screening Visit), OR if the Investigator is concerned that the patient's use of cannabis/THC or alcohol could interfere with patient's ability to provide reliable data or comply with the protocol. Cannabis/THC and alcohol use is otherwise allowed, with caution. The screening drug screen will also test for THC to provide the Investigator with information regarding exposure, and to ensure that all usage is disclosed and taken into consideration when conducting MINI Module J.

9.3. Enrollment of Patients

Before undergoing any study-related screening procedures, each potential patient must provide written informed consent. The Investigator will then determine the potential patient's suitability for the study by interviewing the patient and by performing per-protocol Screening assessments. Pre-randomization Approval by Tonix Pharmaceuticals will be required prior to Visit 2 in addition to satisfying all other eligibility and randomization criteria. If excluded medications are to be withdrawn for the explicit purpose of participation in this study, the patient must have already provided consent and signed an ICF before the withdrawal or down-titration of any medication is initiated.

10. STUDY DRUG MATERIALS AND MANAGEMENT

10.1. Study Drug Packaging, Labeling, and Storage

Study drug supplies will be packaged identically so as to maintain the integrity of the study blind. The study drug bottles will be labeled minimally with the following information: study number TNX-CY-PA201, Sponsor name and address, bottle number, quantity, storage conditions, usage instructions, and caution statements for investigational new drug, ie, Caution: New Drug – Limited by United States Law to Investigational Use, and Keep Out of Reach of Children and Pets.

Each study drug bottle will contain 40 tablets. One bottle will be dispensed to each patient at Visit 2 (Baseline), and then 2 bottles will be dispensed at Visit 3 (Week 2), Visit 4 (Week 6), and Visit 5 (Week 10). This will provide the patient with enough tablets to cover the 2 or 4 weeks of dosing between visits, plus additional tablets to cover loss and/or visit window variability. The patient should be instructed to take all the tablets in one bottle before opening the second bottle. The patient should be instructed to keep this study drug in a safe location out of extreme environmental conditions and out of the reach of children and pets, and be instructed that this drug is not to be taken by any individual other than the study patient. Each patient will also be instructed that they are expected to return both bottles (even if empty) and all unused study drug at each clinic visit; unused drug will be counted to assess compliance with study drug treatment.

Storage of the study drug at the investigational site should be under locked and secure conditions with limited staff access. Study drug should be stored at 20–25°C/68–77°F in a temperature/humidity-monitored room; however, additional details on acceptable brief excursions and other pertinent information will be provided to the site.

10.2. Dosing Instructions

Patients will be instructed to take 1 tablet of randomly assigned study drug TNX-102 SL 2.8 mg or placebo tablet sublingually (under the tongue) each evening at bedtime starting at bedtime on Day 1 (Day of Visit 2) and continuing through Day 14. At the Week 2 Visit, patients will be instructed to increase the dose to 2 tablets at bedtime, administered simultaneously and under the tongue beginning on Day 15 and continuing through the end of the study.

The study drug should be taken at bedtime after teeth brushing and other oral care has been completed. The mouth/sublingual area should be moist at the time of dosing, so the patient should drink a few sips of water prior to dosing, especially if prone to dry mouth. Patients will be instructed to place the 1 or 2 SL tablets under their tongue (if 2, placed simultaneously under tongue) and keep them there until they have dissolved (approximately 90 seconds). They should not swallow, crush, or chew the tablets. Patients should not eat, drink, or chew gum for at least 15 minutes after dosing, and preferably not drink any hot, cold, or acidic beverage until morning. Patients also should not talk for at least 5 minutes after placing the study drug in the mouth (under the tongue). Patients will be reminded that only 2 tablets are allowed per day. Note: If the patient misses a dose, instruct the patient to continue dosing with 2 tablets the next evening; ie, they should not take more to make up for the missed dose.

If the patient reports intolerable side effects that are likely to result in premature discontinuation from the study, then the dose of study drug may be reduced to 1 tablet sublingually nightly, with

Medical Monitor approval. Any reduction in study drug dose must be documented in the case report form (CRF). The goal is for the patient to be on a stable and final dose of study drug starting from the Week 2 Visit, at the highest dose tolerated (preferably 2 tablets daily at bedtime). It is anticipated that only a few patients will require dosage reduction, as TNX-102 SL 5.6 mg has been well-tolerated in previous Phase 3 studies of TNX-102 SL. Moreover, the gradual titration from 1 tablet for the first 2 weeks to 2 tablets for the remainder of the study should help with acclimation to the higher dose.

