10.3. Dispensing Instructions

Each patient who has met the randomization criteria (Section 8.4) will be assigned a double-blind treatment bottle at Visit 2 via the Interactive Response Technology (IRT), with a unique, but otherwise random bottle number that is generated when the study coordinator successfully completes randomization procedures. Patients will take one sublingual tablet each evening at bedtime for the first 2 weeks.

Beginning with the evening of the Week 2 Visit, patients will take 2 sublingual tablets each evening at bedtime, and will continue doing so throughout the course of the study. Only in the event of AEs that might possibly lead to discontinuation can the patient reduce the dose to 1 tablet per evening, with approval of the Principal Investigator and Medical Monitor.

Study treatments at maximum dosage for the double-blind treatment phase are either:

Treatment A: 2 × TNX-102 SL 2.8 mg tablets (“TNX-102 SL”) to be taken sublingually (simultaneously) once daily at bedtime.

Treatment B: 2 × placebo tablet (“placebo”) to be taken sublingually (simultaneously) once daily at bedtime.

In the event that a study drug bottle is lost, a new bottle will be provided by the IRT when appropriately requested by the site and/or the Sponsor or designee.

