11.3. Visit 3 (Week 2)

Visit 3 should occur after 2 weeks of treatment, on Day 15 -4 / +7 days. For those patients unable to return to the site (ie, extenuating circumstances due to COVID-19 pandemic), a telephone visit is an option.

The following assessments and procedures are scheduled for this visit in the following general order:

- Record concomitant medication use
- Examination of the oral cavity. Ensure that this exam includes the sublingual area and that any abnormalities are carefully described on the oral exam source document. (Telephone visit exception – visual exam of the oral cavity is not required – but in addition to standard inquiry about AEs, site staff will inquire specifically if there have been any changes or problems in the oral cavity. Patients reporting any concerning lesion description or painful processes in the oral cavity possibly related to study drug exposure should be strongly urged to come into the clinic for an Unscheduled Visit for oral cavity exam. In circumstances in which, due to the COVID-19 pandemic, it is not possible for the patient to return to the clinic for the Unscheduled Visit exam, a clinician certified by the Sponsor to conduct oral cavity examination should contact the patient by phone and obtain greater history and description of the oral cavity AE by patient, potentially augmented with images of oral cavity taken by the patient and sent to the site for the examining clinician to *textually* document in the oral exam source document. In such cases in which the patient is unwilling or unable to come in, Principal Investigator (PI) and Medical Monitor should also confer on whether study drug should be discontinued.)
- Administer Baseline/Post-Randomization Version of the mMBM
- Administer the “Since Last Visit” version of the C-SSRS. (Telephone visit exception: C-SSRS is administered over the phone)
- Patient should complete the following PROs (Telephone visit exception: all PROs should be mailed ahead of the visit and returned to the clinic after completion via courier):
 - a. SDS
 - b. PROMIS Short Form – Sleep Disturbance
 - c. PROMIS Short Form v1.0 – Fatigue 8a
 - d. PROMIS Short Form v1.0 – Cognitive Function - Abilities
 - e. PGI-C
 - f. ESS
- Administer urine pregnancy test for females of child-bearing potential (processed in-clinic). (Telephone visit exception: urine pregnancy test will be performed at home by patient for women of child-bearing potential).

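### The missed-dose note in Protocol 10.2 is not limited to patients on 2 tablets, so read literally it doubles the next evening's dose for anyone assigned 1 tablet

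*Protocol*

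**What the plan says.** Protocol section 10.2 sets two dose levels. Through Day 14 patients are to "take 1 tablet of randomly assigned study drug TNX-102 SL 2.8 mg or placebo tablet sublingually" each evening, and from Day 15 they take 2 tablets. If side effects threaten discontinuation, "then the dose of study drug may be reduced to 1 tablet sublingually nightly", with Medical Monitor approval. Section 7.1 lets such a patient stay on the lower dose for the rest of the study.

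Section 10.3 repeats the titration step: "Patients will take one sublingual tablet each evening at bedtime for the first 2 weeks". It ties the increase to the visit: "Beginning with the evening of the Week 2 Visit, patients will take 2 sublingual tablets each evening at bedtime".

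The missed-dose note stands in the middle of 10.2, in a paragraph on sublingual technique that covers both 1 and 2 tablets. It reads "If the patient misses a dose, instruct the patient to continue dosing with 2 tablets the next evening", followed by the gloss "ie, they should not take more to make up for the missed dose". Neither the protocol nor the SAP contains another missed-dose rule.

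**The concern.** The note states a tablet number, and that number is right only for patients assigned 2 tablets. A patient on 1 tablet who misses an evening would, on the literal text, be told to take 2 the next evening. That conflicts with the 1-tablet regimen in 10.2 and 10.3, and with the note's own ban on making up the missed dose.

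Two groups are exposed:

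- **Everyone in titration.** The first two weeks at 1 tablet are meant to help patients acclimate to the higher dose.
- **Patients reduced for intolerability.** Under 7.1 a return to 2 tablets is a re-challenge that the Investigator must judge clinically warranted. The note would bring it about after any missed dose, without that judgment.

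What is at stake is tolerability and a minor safety matter. No statistical quantity depends on it.

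**Working it through.** **Inputs**

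- Tablet strength 2.8 mg; full dose 2 tablets = 5.6 mg (Protocol 7.1, 10.2).
- 1 tablet on Days 1–14 and 2 tablets on Days 15–98 (Protocol Synopsis, dosage).
- Visit 3 timing: "Visit 3 should occur after 2 weeks of treatment, on Day 15 -4 / +7 days" (Protocol 11.3), so Day 11 to Day 22.
- Supply: "Each study drug bottle will contain 40 tablets" (Protocol 10.1), with one bottle dispensed at Visit 2.

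**Dose on the evening after a miss**

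The plan's own equivalence reproduces: 2 × 2.8 = 5.6 mg.

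| Assigned dose | Dose assigned that evening | Dose under the literal note | Ratio |
|---|---|---|---|
| 2 tablets | 5.6 mg | 5.6 mg | 1.0 |
| 1 tablet | 2.8 mg | 5.6 mg | 2.0 |

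These are active-arm doses. In the placebo arm only the tablet number doubles.

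**Conflict with the note's second clause**

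Over the two evenings, a 1-tablet patient is assigned 1 + 1 = 2 tablets. Under the literal note the patient takes 0 + 2 = 2, so the missed tablet is made up in full.

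**Titration evenings on which this can happen**

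These are the 1-tablet evenings less Day 1, which has no earlier dose to miss.

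- Nominal schedule: Days 2–14 = 13 evenings; 13/98 = 13% of dosing days.
- Increase on the evening of Visit 3, visit on Day 11: Days 2–10 = 9 evenings.
- Increase on the evening of Visit 3, visit on Day 22: Days 2–21 = 20 evenings.

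These counts are opportunities, not rates. Each also needs a missed dose the evening before.

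**Would supply prevent it?**

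No. After 14 nights at 1 tablet the bottle holds 40 − 14 = 26 spare tablets. After 21 nights (Visit 3 on Day 22) it holds 40 − 21 = 19.

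**Would it be noticed?**

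- *Tablet count (Protocol 10.5).* Over 14 nights with one miss followed by 2 tablets, use is 12 × 1 + 0 + 2 = 14, against 14 expected. Either way 26 are returned, so no discrepancy query arises.
- *Diary (Protocol 12.1.8).* The daily question on the number of tablets taken would record it if answered. The SAP 12.3 count of days on each dose would then be correct. The SAP 12.3 compliance percentage would show the missed day but not the doubled one, because it ignores the number of tablets.

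**The case against.** The best answer is that no careful reader would apply the note to a 1-tablet patient. A patient cannot continue with 2 tablets when the current dose is 1, and the closing clause forbids taking more to compensate. Other sections point the same way. Section 7.1 tells patients to change dose only in consultation with the Investigator, and 11.3 has the increase explained and confirmed at the Week 2 Visit. The note is addressed to site staff, so harm requires staff to pass on the wrong number. Even then the result is one evening at the trial's target dose, which the protocol describes as well tolerated in earlier Phase 3 studies.

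Most of this stands. The intent is clear, and the consequence is small. Calling the fault an omitted qualifier rather than a deliberate choice is also fair.

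It does not make the stated number right. The daily limit of 2 tablets in 10.2 permits the doubling. The Investigator-consultation rule is weak protection here, because the note is itself something the site is told to instruct: a patient who follows it would reasonably think the dose was site-directed. About 30 sites must relay this text, and for 1-tablet patients they have to infer that the printed number does not apply. What patients are actually told may also depend on bottle labels and patient materials, which are not among the documents.

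**Conclusion.** The concern holds. The note is wrong as written for patients assigned 1 tablet: it gives twice the assigned dose (5.6 mg instead of 2.8 mg in the active arm) on the evening after a miss, and contradicts both the regimen and its own second clause.

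The impact is minor. It rests on the literal reading being followed, on a missed dose the evening before, and on the patient being on 1 tablet at the time. In titration that means up to 13 evenings nominally, or 9 to 20 across the Visit 3 window if the increase follows the visit as 10.3 states. For dose-reduced patients it can follow any miss while on 1 tablet; the protocol expects only a few such patients. The documents give no missed-dose rate, so the number of patients affected cannot be stated. Alpha, power, the estimand and the primary analysis do not change.

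**What to change.** Replace the note in Protocol 10.2 with wording tied to the current assignment, for example: *After a missed dose, tell the patient to resume the currently assigned dose (1 or 2 tablets) the next evening and not to take extra tablets to compensate.* Patients on 2 tablets are unaffected, the rule becomes correct for patients on 1 tablet, and the ban on make-up dosing stays.

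The cost is one sentence in the protocol, plus the same correction in any patient-facing instructions that repeat the note. Design, sample size and analysis need no change.

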10.3. Dispensing Instructions

Each patient who has met the randomization criteria (Section 8.4) will be assigned a double-blind treatment bottle at Visit 2 via the Interactive Response Technology (IRT), with a unique, but otherwise random bottle number that is generated when the study coordinator successfully completes randomization procedures. Patients will take one sublingual tablet each evening at bedtime for the first 2 weeks.

Beginning with the evening of the Week 2 Visit, patients will take 2 sublingual tablets each evening at bedtime, and will continue doing so throughout the course of the study. Only in the event of AEs that might possibly lead to discontinuation can the patient reduce the dose to 1 tablet per evening, with approval of the Principal Investigator and Medical Monitor.

Study treatments at maximum dosage for the double-blind treatment phase are either:

Treatment A: 2 × TNX-102 SL 2.8 mg tablets (“TNX-102 SL”) to be taken sublingually (simultaneously) once daily at bedtime.

Treatment B: 2 × placebo tablet (“placebo”) to be taken sublingually (simultaneously) once daily at bedtime.

In the event that a study drug bottle is lost, a new bottle will be provided by the IRT when appropriately requested by the site and/or the Sponsor or designee.

10.4. Release of Clinical Study Supplies to the Investigator

Tonix or Tonix’s designee’s Standard Operating Procedures for releasing clinical trial supplies to the site will be followed.

10.5. Study Drug Accountability and Reconciliation

All patients will be expected to bring their bottles of study drug with them to all study visits (including empty bottles). At each study visit, the site staff will inspect the drug bottles and perform a count of the tablets remaining in the bottles and document this in the patient’s record. An assessment of drug adherence should be done by the study staff to ensure that the patient understands all dosing instructions and is taking the drug as prescribed. Patients will be asked for an explanation if the count of returned study drug tablets indicates a discrepancy between the expected number of tablets dosed and the number returned in the bottles. If it is found that the patient is not taking the study drug as expected, the patient will be re-c counseled with instructions, and this should be noted in the patients’ records. A deviation should be recorded on

any patient who is less than 70% compliant with dosing between visits, and a Medical Monitor should be contacted. In addition, if a patient fails to return >8 tablets within a 4-week (or >4 in a 2-week period), the PI is required to assess the patient for any potential drug abuse, misuse, or diversion. This assessment should be documented and reported within the Drug Accountability case report form.

Tonix or its designee will perform drug accountability, which entails reconciliation between the amount of drug shipped to the study site, study drug assigned and dispensed to the patient (including returned unused assigned study drug), and study supplies that were never dispensed and/or assigned to patients.

